The primary efficacy endpoint is evaluation of the Genomic Prostate Score (GPS) after intervention with Noni extract. All subjects who meet eligibility criteria, have taken at least one dose of study medication, and have a post-treatment biopsy will be considered

evaluable for the primary efficacy endpoint. Tissue from prostate biopsies will be evaluated by a pathologist affiliated with the UHCC at screening and post-intervention with study agent. Representative slides from the diagnostic biopsy (at least 8 cores) and from biopsy specimens at 12 months post-intervention (at least 8 cores) are required for analysis. Biopsies will be obtained, and formalin-fixed. Paraffin-embedded prostate biopsy specimens from all patients included in this study will be prepared at each site, where original slides will be stained with H&E. Then biopsy samples will be shipped to Genomic Health to undergo Oncotype DX Prostate Cancer Test with the assessment of Genomic Prostate Score (GPS). The H&E-stained sections will be evaluated by light microscopy for presence of cancer, extent of cancer, grade of cancer by a centralized pathologist affiliated with UHCC, using uniform established standards.

Progression of Disease

PSA progression:

a) PSA doubling time (DT) < 2 years, based on at least 3 separate measurements over a minimum of 6 months

Histological progression:

- a) > 3 cores positive for prostate cancer;
- b) Gleason pattern predominant 4 or higher (i.e. Gleason 7 (4+3) or higher) in the rebiopsy specimen of the prostate performed at 12 months as per protocol

Clinical progression:

- a) more than twice increase in the product of the maximum perpendicular diameters of the primary lesion as measured radiographically
- b) local progression of prostate cancer requiring transurethral resection of the prostate
- c) development of ureteric obstruction
- d) radiological and/or clinical evidence of distant metastasis

Secondary Endpoints

The effects of Noni extract on serum PSA during the course of the study will be noted.

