The incidence and severity of AEs occurring during intervention will be noted. All AEs that are reported by the subject, detected during a visit, physical examination, or laboratory work-up will be recorded in the participant's medical record and recorded on the CRF. All AEs that occur after study enrollment will be recorded on the AE CRF whether or not related to study agent. The following information will be captured for each AE: date reported; CTCAE Term (v 4.0); onset and resolution date; severity grade; attribution to study agent; whether or not the event was reported as an SAE; action taken; whether or not the subject dropped due to the AE; outcome; and comments.

Treatment related changes in angiogenesis (CD34), proliferation (Ki-67) and apoptosis (TUNEL) will be reported comparing initial diagnostic prostate biopsy and 12 month prostate biopsy provided sufficient tissue is available.

QoL and LUTS will be noted during the course of the study.

OFF DRUG CRITERIA

Participants may stop taking study agent for the following reasons:

- after completing the protocol-prescribed intervention
- at the discretion of the investigator
- AE or SAE requiring dose interruption
- inadequate agent supply
- noncompliance with study requirements
- medical contraindication

Off Study Criteria

If the subject never took study medication (e.g., does not meet eligibility criteria or withdraws consent prior to enrollment) the only activity required to remove the subject from the study is to complete the Off Study CRF. If the subject was enrolled and received study medication, post-intervention procedures according to the schedule of events should be completed to the extent possible.

Off-study criteria include:

- not meeting enrollment (eligibility) criteria
- the protocol intervention and any protocol-required follow-up period is completed
- experiencing an AE or SAE
- lost to follow-up
- taking a concomitant medication
- medical contraindication prohibiting further study participation
- discovery of a pre-existing condition not observed at baseline eligibility
- withdrawal of consent
- disease progression
- protocol non-compliance (i.e., visit schedule, dose administration, etc.)
- at the discretion of the investigator
- death

Study Termination

The study sponsor has the right to discontinue the study at any time.

SPECIMEN MANAGEMENT

Laboratories

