Study samples (plasma for scopoletin and serum for banking) will be processed and packaged at the UHCC. All study samples (tissue slides, paraffin blocks, plasma for scopoletin analysis, serum for banking) will be shipped to [name] attention at UH Cancer Center. All samples collected will be labeled with a tough tag using a unique specimen number to include the (a) site number, (b) subject registration number, (c) visit number, (d) and specimen ID to permit computerized tracking of master and daughter specimens. All blood and tissue sample shipped to the UH Cancer Center for storage and banking will be addressed as follows:

[name]., M.B.A., F.A.C.S. University of Hawaii Cancer Center [name] Contact: [name].

Sample Banking

A human tissue repository consisting of prostate tissue biopsies from very low risk and low risk prostate cancer obtained from all subjects at baseline screening and 12 months, to permit the testing of hypotheses anticipated in future research for which external NIH funds will be sought. Serum samples will be similarly stored for future research.

Sample Tracking

All samples collected will be labeled with a unique specimen number. This information will be entered into an existing, customized software program for tracking. The master log, maintained at the UH Cancer Center, will indicate the location of each sample by storage box, freezer shelf, and freezer.

Plasma Scopoletin Analysis

Will be performed by HPLC-EC completed at enrollment, 3, 6, 9 and 12 months

Page 30 of 38

DATA AND SAFETY MONITORING

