Study Design/Endpoints

The proposed clinical study is a Phase II, single arm, open label trial in men > 55 years of age with biopsy proven (minimum of 8 cores) very low risk or low risk prostate cancer (confirmed by Oncotype DX Prostate Cancer Test); a total of 30 men will be enrolled. Subjects will receive Noni capsules (6,000 mg/day) for 12 months. After the planned 12-

month intervention is complete (or if a biopsy is indicated earlier), a repeat prostate biopsy will be performed for post-intervention endpoint measurements. The primary endpoint of the study is a comparison of the Genomic Prostate Score (GPS) after treatment with Noni extract. Furthermore, pelvic MRI with contrast will be performed and the size of any lesion calculated. Radiologic report of the MRI should be collected as it is a source document. Other endpoints include: investigating progression of prostate cancer after treatment with Noni extract, investigating modulation of serum PSA after treatment with Noni extract, reporting the tolerability of Noni extract in men with very low risk and low risk prostate cancer, investigating key molecular changes associated with angiogenesis, proliferation or apoptosis and reporting quality of life elements.

ETHICAL AND REGULATORY CONSIDERATIONS

This study is to be conducted according to US and international standards of Good Clinical Practice (FDA Title 21 part 312 and International Conference on Harmonization guidelines), applicable government regulations and Institutional research policies and procedures.

Informed Consent

All potential study participants will be given a copy of the IRB-approved Informed Consent to review. The investigator or qualified study staff will explain all aspects of the study in lay language and answer all questions regarding the study. If the participant decides to participate in the study, he will be asked to sign the Informed Consent document. The subject is considered enrolled in the study from the time the informed consent document is signed. Any and all AEs and concomitant medication taken by the study participant must be captured up to the time of termination from the study. The study agent(s) will not be released to a participant who has not signed the Informed Consent document. Subjects who refuse to participate or who withdraw from the study will be treated without prejudice.

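### No step masks the readers of the tissue markers, or of the histological part of progression, to time point, and the specimen label carries the visit number

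*Combined protocol and SAP*

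**What the plan says.** **Labels.** Specimen Management, Shipping Instructions: "All samples collected will be labeled with a tough tag using a unique specimen number". That number is to include "a) site number, (b) subject registration number, (c) visit number, (d) and specimen ID", for computerized tracking. The same paragraph counts tissue as a study sample: "All study samples (tissue slides, paraffin blocks, plasma for scopoletin analysis, serum for banking".

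**Design.** Statistical Considerations, Study Design/Endpoints: "The proposed clinical study is a Phase II, single arm, open label trial".

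**Histology.** Under Primary Endpoint, biopsy tissue is "evaluated by a pathologist affiliated with the UHCC at screening and post-intervention with study agent". The H&E sections are read for "presence of cancer, extent of cancer, grade of cancer by a centralized pathologist affiliated with UHCC, using uniform established standards". Under Progression of Disease, the histological criteria are more than 3 positive cores, or predominant Gleason pattern 4 or higher in the month-12 rebiopsy. PSA and clinical criteria are separate routes to progression.

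**Markers.** Secondary Endpoints: "Treatment related changes in angiogenesis (CD34), proliferation (Ki-67) and apoptosis (TUNEL) will be reported comparing initial diagnostic prostate biopsy and 12 month prostate biopsy", on condition that there is enough tissue. Prostate Cancer Pathology has a molecular laboratory stain slides from the same blocks, and does not say who scores them.

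**Masking.** No section mentions masked reading, recoded slides, random reading order or a second read. The uniform standards are the only safeguard named.

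**The concern.** Extent of cancer, Gleason pattern and staining indices all involve judgement. Someone who follows the plan as written will probably know whether a slide is diagnostic or post-treatment, from the label or simply from when the slide arrives. The protocol also sets an expectation: its background says that earlier evidence attests to the efficacy of noni in modulating relevant pathways.

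For the markers, the only comparison is diagnostic against month 12. With no control arm, a systematic difference in how the two sets are scored cannot be told apart from a drug effect. For progression the exposure is smaller, because the criteria are fixed thresholds and not differences from baseline. Knowing that a slide is post-treatment could still tip a borderline core or Gleason call. The rate of progression is listed among the primary objectives, although Study Design/Endpoints places it among the other endpoints.

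**Working it through.** **Step 1: can a reader see the time point?** The labelling rule covers all samples and includes the visit number. Slides and blocks are named among the samples. The trial is open label. One pathology evaluation takes place at screening and the other after the intervention, so workflow also reveals timing. No provision counteracts any of this. The conclusion is an inference from these statements together; no sentence says that readers are unmasked.

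**Step 2: which endpoints depend on such a reading?**

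| Endpoint | Source of the value | Exposure |
|---|---|---|
| Genomic Prostate Score | Outside testing company | Not part of this point |
| CD34, Ki-67, TUNEL | Stained slides, scorer not named | Direct: a before-after comparison |
| Histological progression | Central pathologist, thresholds on the rebiopsy | Lesser: borderline calls only |
| PSA and clinical progression | Laboratory, imaging, clinical events | None from the slide read |

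**Step 3: an illustration for a marker.** The plan gives no figure for reading bias, so there is none to reproduce. The planned number of pairs is 30 (Sample Size). That figure was derived for gene expression, and masking would not alter it. Assume:
- no true change in the marker;
- a two-sided 5% paired t-test, which the plan does not specify for markers;
- an average reading shift of d standard deviations of the paired difference.

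The rejection probability is P(|T| > t(0.975, n−1)), where T is noncentral t with n−1 degrees of freedom and noncentrality d√n.

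| n | Critical t | d | d√n | False-positive rate |
|---|---|---|---|---|
| 30 | 2.045 | 0.1 | 0.548 | 0.0827 (8%) |
| 30 | 2.045 | 0.2 | 1.095 | 0.1852 (19%) |
| 30 | 2.045 | 0.3 | 1.643 | 0.3555 (36%) |
| 15 | 2.145 | 0.1 | 0.387 | 0.0651 (6.5%) |
| 15 | 2.145 | 0.2 | 0.775 | 0.1116 (11%) |
| 15 | 2.145 | 0.3 | 1.162 | 0.1915 (19%) |

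The rows for n = 15 are an assumed case of tissue shortage. Criteria for Evaluation and Endpoint Definition warns that tissue may not suffice for all markers and ranks them after the Oncotype test.

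**Step 4: an illustration for progression.** One changed borderline call moves the rate by at most 1/30 = 3.3 percentage points. It moves it by nothing if that man already counts as progressed on another criterion.

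**The case against.** The strongest reply is that the label rule is about shipping and tracking and says nothing about what a reader sees. H&E slides are prepared and stained at the sites, and diagnostic biopsies can predate consent, so those slides may carry other labels. This stands as a limit. A reader might infer that the protocol positively requires unmasked reading, and the text does not go that far. What remains is that no section provides masking and the written label would work against it. Deleting the visit number alone would not help, because workflow shows the timing too.

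A second tempting inference is that the primary efficacy result is compromised. The documents do not support it: the Genomic Prostate Score is produced by an outside company and is not a judgement by this pathologist. It is likewise too much to say that progression is a before-after contrast, or that the staining laboratory is known to do the scoring.

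Third, the false-positive rates describe a test that is not planned, with assumed shifts, on markers that are exploratory and depend on tissue. All of that stands, so the rates show sensitivity only and do not estimate the bias in this trial.

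**Conclusion.** The point holds with a limited scope. The plan leaves the CD34, Ki-67 and TUNEL changes open to reader expectation and, to a lesser extent, the core-count and Gleason components of progression. It rests on the inference that readers can tell the time point, drawn from the label content, the open-label design, the workflow and the absence of any masking step.

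The size is unknown. Under the stated assumptions the false-positive rate for a marker would run from 6.5% (0.1 SD, 15 pairs) to 36% (0.3 SD, 30 pairs), against a nominal 5%. The effect on progression is at most 3.3 percentage points per changed call in 30 men. Masking to treatment is impossible with one arm, but masking to time point is feasible. This is a worthwhile, inexpensive improvement and not a flaw in the primary endpoint.

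**What to change.** For the endpoint read only:

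- Cover or replace the label with a random code that hides subject and visit. Hold the key in the master log that Sample Tracking already provides.
- Stain diagnostic and month-12 slides in the same batches. Name the marker scorer, who scores under code.
- After the last month-12 biopsy, have the same central pathologist read coded sets from all men and both time points, pooled in random order. Use this read for the histological criteria in the progression analysis.
- Do not place a man's two sets side by side. Eligibility requires Gleason 6 or lower at diagnosis, so within a pair a set that has progressed in grade identifies itself as month 12.
- Leave the eligibility and clinical-care reads as they are.

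The cost is relabelling, later marker results and one coded repeat look at up to about 60 slide sets: 30 diagnostic, plus 30 month-12 if the same pathologist also issues the clinical report. No additional reader, biopsy or patient is needed. Masking will not be perfect: the pathologist may remember a case, and a clearly high-grade set can be guessed to be month 12. Borderline calls, where expectation matters most, would be better protected.

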Clinical records for all participants, including CRFs, all source documentation (containing evidence to study eligibility, history and physical findings, laboratory data, results of consultations, etc.), as well as IRB records and other regulatory documentation will be retained by the each site investigator in a secure storage facility in compliance with HIPAA, OHRP, FDA regulations, and ICH requirements unless the standard at the site is more stringent for a minimum of two years. The sponsor will be notified prior to the planned destruction of any materials. The records should be accessible for inspection and copying by authorized persons of the Food and Drug Administration.

STATISTICAL CONSIDERATIONS

Sample Size

A number of methods have been developed to extract useful and robust information from genomic data sets. However, attention also has to be paid to the experimental design before the investigator completes the experiment. One of the principal limitations of previous molecular profiling studies is the relatively low numbers of samples analyzed. We needed to estimate the sample size requirements necessary to satisfy a specified false discovery rate and power given various biological and experimental variations. We estimated variance based on previous biomarker work. Sample size for this study was estimated according to equation

$$n = \frac{\sigma^2 (Z_{1-\alpha/2} + Z_{1-\beta})}{(\mu_1 - \mu_0)^2}$$

 $n = \frac{\sigma^2 (Z_{1-\alpha/2} + Z_{1-\beta})^2}{(\mu_1 - \mu_0)^2}$ where σ^2 is the variance of the gene expression, $Z_{1-\alpha/2}$, $Z_{1-\beta}$ are the $(1-\alpha/2)$ th, $(1-\beta)$ th quantile of the standard normal distribution respectively, with α being the type I error and β being the type II error. All signal values were log2

transformed. Variance was calculated for each protein. The 90th percentile variance value (3.94) was chosen be the σ^2 in equation. In order to detect a 2-fold change in the expression level, $(\mu_1 - \mu_0)^2$ in equation will be 1. We used 0.05 as the significance level. The estimated sample size is 30 for 80% power. Each patient will have 2 sets of genomic data (baseline and 12 months) collected over the course of the study to monitor a unique genomic signature associated with Noni extract in very low risk or low risk prostate cancer. The accrual rate is expected to be approximately 1 to 2 patients / month. Thus, it is expected to take about 15-30 months to accrue the 30 patients.

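### The 80% power at 30 men is for one expression marker, not for GPS, and the plan's lists disagree on whether progression is primary

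*Combined protocol and SAP*

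**What the plan says.** **Sample size.** The only power calculation is under Statistical Considerations, Sample Size. Its aim is a size "necessary to satisfy a specified false discovery rate and power given various biological and experimental variations". It uses a normal-theory equation in which σ² "is the variance of the gene expression". The value for σ² comes from previous biomarker work on the log2 scale: "Variance was calculated for each protein. The 90th percentile variance value (3.94) was chosen be the" σ² of the equation. The effect is set as follows: "In order to detect a 2-fold change in the expression level", the squared difference is 1. With a significance level of 0.05, the result is "The estimated sample size is 30 for 80% power". GPS is not mentioned in this calculation.

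**Primary endpoint.** Under Criteria for Evaluation and Endpoint Definition, Primary Endpoint: "The primary efficacy endpoint is evaluation of the Genomic Prostate Score (GPS) after intervention with Noni extract". Statistical Considerations, Study Design/Endpoints, also names GPS as the primary endpoint and speaks only of a comparison after treatment.

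**Progression and PSA.**
- The synopsis lists three items under primary efficacy: gene expression changes on the Oncotype test, tumor progression, and PSA doubling time.
- Objectives, Primary, lists GPS with its associated gene expression changes, and the rate of progression at one year. PSA is a secondary objective.
- The endpoint-definition section sets out progression criteria between its primary and secondary headings without giving them a status. Under Secondary Endpoints it says: "The effects of Noni extract on serum PSA during the course of the study will be noted".
- Study Design/Endpoints puts progression and PSA among the other endpoints.

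**The concern.** A reader who meets one sample size, one power figure and one named primary endpoint will take the 80% to be power for that endpoint. Here it is not. The plan never says what change in GPS 30 men could detect, in what units, or by what test. A GPS result that shows no difference could therefore not be set against any change the trial was designed to find.

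Two further matters affect what the trial may claim. The sample-size text invokes a false discovery rate, which suggests that testing many genes has been allowed for. And current sections of the same document support calling progression either a primary result or not.

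**Working it through.** **Inputs from Statistical Considerations, Sample Size:** σ² = 3.94 (log2 scale, 90th percentile across markers); difference = 1 log2 unit; α = 0.05, two-sided because the equation uses the 1−α/2 quantile; power 80%; n = 30.

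**1. The plan's own figure.** n = σ²(z₀.₉₇₅ + z₀.₈₀)² / difference² = 3.94 × (1.95996 + 0.84162)² / 1 = 3.94 × 7.849 = 30.92. That is 31 when rounded up, against 30 stated. The equation also appears without the square, which would give 3.94 × 2.80158 = 11.04. Only the squared form matches the plan, and the other may be an artefact of reading the PDF.

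**2. Power of that calculation at 30, if 3.94 is the variance of the paired change.** Normal formula: Φ(√(30/3.94) − 1.95996) = Φ(2.759 − 1.960) = 78.8%. With a paired t-test (assumed, since the plan names no test), the standardised effect is 1/√3.94 = 0.504 and power on 29 degrees of freedom is 76.0%.

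**3. The same, if 3.94 is the variance of a level.** The variance of the paired change is then 2 × 3.94 × (1 − ρ), where ρ is the correlation between baseline and month 12. The documents do not give ρ, so the values below are assumed.

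| Assumed ρ | Variance of change | n for 80% | Normal-formula power at 30 |
|---|---|---|---|
| 0 | 7.88 | 62 | 50% |
| 0.25 | 5.91 | 47 | 62% |
| 0.5 | 3.94 | 31 | 79% |
| 0.75 | 1.97 | 16 | 97% |

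The text does not say which reading applies. It also refers the variance to gene expression in one sentence and to proteins in another.

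**4. False discovery rate.** The equation contains α = 0.05 for one comparison and no term for the number of genes tested. No rate is stated. The false discovery rate therefore played no part in reaching 30.

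**5. GPS.** Neither an SD of the GPS change nor a target change is given, so no power for GPS can be computed. What 30 pairs give can be stated in SD units, assuming a two-sided 0.05 paired t-test on the within-man change:
- Smallest mean change with 80% power: 0.53 SD of the change.
- 95% CI half-width: t₀.₉₇₅,₂₉/√30 = 0.37 SD.
- Power for assumed true changes of 0.3, 0.4, 0.5, 0.6 and 0.8 SD: 36%, 56%, 75%, 89% and 99%.
- For assumed SDs of change of 5, 10 and 15 GPS points, the detectable change is 2.6, 5.3 and 7.9 points.

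**6. Status of each endpoint.**

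| Section | GPS / gene expression | Progression | PSA |
|---|---|---|---|
| Synopsis | primary (gene expression) | primary | primary (doubling time) |
| Objectives | primary (both) | primary | secondary |
| Endpoint definition | primary (GPS) | not stated | secondary |
| Study Design/Endpoints | primary (GPS) | other | other |

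The substantive conflict is over progression. PSA doubling time is out of line only in the synopsis.

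**The case against.** The strongest reply is that GPS and gene expression are not separate matters in this plan. The primary objective names GPS with its associated gene expression changes, and the synopsis words the endpoint as expression changes on the same test. On that view the calculation does address the primary objective. This stands in part: it covers the gene-level half. The documents give no link from a 2-fold change in one marker to a change in GPS, so the power does not carry over.

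The marker calculation is also sound as arithmetic, since 30.92 against 30 is rounding. Because 3.94 is a 90th percentile, most markers would have more power than the figure given, before any adjustment for multiple testing. Both points are right.

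A reader might go further in four directions that the documents do not support.
- *The trial is underpowered for GPS.* Without an SD and a target, this cannot be shown, and neither can the opposite.
- *Marker power is only about 50%.* That needs 3.94 to be a level variance with zero correlation, and neither is stated.
- *Missing score pairs will erode the sample.* The evaluability rule asks only that men "have taken at least one dose of study medication, and have a post-treatment biopsy will be considered" evaluable, besides meeting eligibility. But inclusion criterion 2 requires a GPS at entry, the Replacement section replaces men without usable paired biopsies, and the Oncotype test has first call on scarce tissue. At most, the replacement wording needs tightening.
- *The primary endpoint is open to free choice after the data are seen.* The room is limited, because the endpoint-definition section and the study-design text both name GPS.

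**Conclusion.** The point holds as an unsupported power statement and a contradiction between current sections, and should be fixed. The stated 80% belongs to one expression marker at an unadjusted 0.05. For GPS, the endpoint named as primary in the two sections that define it, the plan offers no SD, target change, test or power. The claim about the false discovery rate has no counterpart in the calculation. Progression is primary in two places and an other endpoint in a third.

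The numerical shortfall in the marker calculation is small (78.8% against 80%) if 3.94 is the variance of the paired change. If it is a level variance, the answer depends on a correlation that the plan does not give. The GPS figures assume a paired t-test with 30 complete pairs. They hold for any endpoint so analysed, so they describe precision and say nothing on whether 30 is enough.

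**What to change.** All changes are to text and leave enrolment as it is.

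1. Reconcile the synopsis and objectives with the endpoint-definition and study-design sections. The simplest form is change in GPS from baseline to 12 months as the single primary endpoint, with progression and PSA doubling time secondary. If the sponsor keeps progression co-primary, state a multiplicity rule.
2. In Sample Size, say that the 80% figure is for a single expression marker and not for GPS. Say whether 3.94 is the variance of a level or of the paired change, and of gene or protein. If it is the paired-change variance, restate power at 30 as about 79% by the plan's formula (76% if a paired t-test is used). If it is a level variance, give the correlation and the resulting power.
3. Delete the false discovery rate claim, or apply a stated level and method, such as Benjamini-Hochberg, to the gene-level tests.
4. Name the GPS analysis and state what 30 pairs give, for example: *Within-man change in GPS will be analysed by a two-sided paired t-test at 0.05. With 30 pairs this has 80% power for a mean change of 0.53 SD of the within-man change, with a 95% CI half-width of 0.37 SD. This describes precision and does not by itself show that 30 is adequate.* If the sponsor holds an SD for GPS change, add the detectable change in GPS points and say whether it is worth detecting.
5. As a minor addition, let the replacement rule cover a biopsy that yields no GPS.

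The cost is a text amendment. The sponsor must choose a GPS test and trace the source of 3.94, the stated marker power may change, and progression may lose its primary status. For PSA doubling time only the synopsis changes.

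### The plan's formula gives 31 men, not 30, for 80% power, and the power at 30 pairs depends on an unnamed test and on which variance 3.94 is

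*Combined protocol and SAP*

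**What the plan says.** The only power statement is in Statistical Considerations, Sample Size: "The estimated sample size is 30 for 80% power". It rests on a normal-quantile formula, introduced with "Sample size for this study was estimated according to equation". The inputs follow in the same section:

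- Significance level: "We used 0.05 as the significance level". The formula uses the 1 − α/2 quantile, so the calculation is two-sided, although the text does not say so in words.
- Effect: "In order to detect a 2-fold change in the expression level", which is 1 unit on the log2 scale, so the squared difference is 1.
- Variance: "The 90th percentile variance value (3.94) was chosen be the σ^2 in equation". The section defines this symbol as the variance of gene expression and says that it was calculated protein by protein.
- Design: "Each patient will have 2 sets of genomic data (baseline and 12 months"). The sample-size entry after the Schema asks for 30 subjects with paired biopsies, and the Replacement section replaces men whose paired biopsies are unavailable.

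No section names the test for the before-and-after comparison. Study Design/Endpoints says only that the primary endpoint is a comparison of the GPS after treatment.

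**The concern.** There are three separate questions. Does the formula return 30 when the plan's inputs are put in? The formula treats the variance as known, whereas an analysis of 30 differences would ordinarily estimate it, so how much power is lost? And is 3.94 the quantity the formula needs? With one group measured twice, the variance that matters is that of each man's change, whereas the text describes the variance of expression itself.

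This is the trial's only power figure. If the result is null, readers will use it to judge what size of change the trial could have missed. A figure with unstated conditions does not support that judgement.

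**Working it through.** **Inputs** (all from the Sample Size section): σ² = 3.94, so SD = 1.985; difference δ = 1 log2 unit; α = 0.05 two-sided, z = 1.95996; power 80%, z = 0.84162; n = 30. The between-visit correlation ρ is not given, so the values below are assumptions.

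**1. The plan's own figure.** n = σ²(z₁₋α/₂ + z₁₋β)²/δ² = 3.94 × (1.95996 + 0.84162)² = 3.94 × 7.849 = 30.92, which rounds up to 31. Rounded quantiles (1.96 + 0.84) give 30.89, still 31. The equation also appears once without the square. That form would give 11.0, and a one-sided 0.05 would give 24.4, so the two-sided squared form is clearly the one used.

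Power at 30 by the same formula: Φ(√30/1.985 − 1.96) = Φ(2.759 − 1.960) = Φ(0.799) = 78.8%. The change detectable with 80% power is 2.8016 × √(3.94/30) = 1.015 log2 units, or 2.02-fold.

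**2. Paired t-test, taking 3.94 as the variance of the within-man change.** Noncentral t with n − 1 degrees of freedom and noncentrality √n/1.985:

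| Pairs | Normal formula | Paired t-test |
|---|---|---|
| 30 | 78.8% | 76.0% |
| 31 | 80.1% | 77.5% |
| 32 | 81.3% | 78.8% |
| 33 | 82.5% | 80.1% |

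At 30 pairs the t-test reaches 80% power for a change of 1.0505 log2 units, and 2^1.0505 = 2.07-fold.

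**3. If 3.94 is the variance at one time point.** With equal variances at the two visits, Var(change) = 2 × 3.94 × (1 − ρ):

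| Assumed ρ | Var(change) | t-test power, 30 pairs | Pairs for 80% (t-test) |
|---|---|---|---|
| 0 | 7.88 | 47% | 64 |
| 0.25 | 5.91 | 59% | 49 |
| 0.5 | 3.94 | 76% | 33 |
| 0.75 | 1.97 | 96% | 18 |

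Only at ρ = 0.5 do the two readings of 3.94 coincide. The t-test reaches 80% at 30 pairs when Var(change) is 3.57, which corresponds to ρ of about 0.55 (1 − 3.57/7.88).

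**The case against.** The strongest reply is that the stated figure is essentially reproduced. By the plan's own method the gap is one patient and 1.2 percentage points, the text calls the sample size an estimate, and planning with a normal approximation is common. That stands: taken alone, the rounding is minor.

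A reader might go further and infer that the trial really has 76% power, or that 80% is simply optimistic. The documents support neither. The 76% needs a paired t-test, which the plan does not name, and it needs 3.94 to be the variance of the change, which the plan does not say. With a single-time-point variance and a correlation above about 0.55, the t-test exceeds 80% at 30 pairs.

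The plan also has a conservative element: 3.94 is the 90th percentile across proteins, so about 90% of those markers have that variance or less, and at least the calculated power. A variance 9% lower (3.57) already gives 80% by t-test. That is a fair reason not to call the figure optimistic. It does not settle which variance was tabulated, because the percentile was taken over the same undefined quantity.

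Finally, the calculation concerns one marker on a log2 scale, whereas the primary endpoint is the GPS. Changing 80% to another number would not give the GPS a power statement, and a restated figure should not suggest that it does.

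**Conclusion.** The point holds as a correction to the stated number and its missing conditions. On the plan's own method, 80% power needs 31 men, and 30 men give 78.8%. Under two conditions that the plan does not state (a paired t-test, and 3.94 as the variance of the within-man log2 change), 30 pairs give 76.0%, and 33 are needed for 80%.

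What 3.94 measures matters far more than the rounding or the choice between normal and t. If it is a single-time-point variance, power at 30 pairs runs from 47% to 96% over assumed correlations of 0 to 0.75. The documents give no correlation, so the direction of any error is unknown. All these figures assume equal variances at the two visits where ρ is used, normally distributed log2 changes, a single marker and an unadjusted two-sided 0.05.

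**What to change.** Keep 30 pairs and replace the power sentence with wording such as:

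> 30 evaluable pairs give about 79% power by the normal formula (76% by a paired t-test, two-sided 0.05) for a 2-fold change in a single marker, if the variance of the within-man log2 change is 3.94.

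Then:

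- Name the test that will be used for the before-and-after comparison.
- State whether 3.94 is the variance of the within-man change or of expression at one time point. If it is the latter, give power over a range of correlations, as in the second table above.
- Say that the figure applies to one marker at the 90th-percentile variance, that markers with lower variance have more power, and that it is not a power statement for the GPS.

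The cost is a few lines of text and one check of the earlier biomarker data to identify the variance. No extra patients or biopsies are needed. The downside is that the headline power looks slightly less favourable under the stated condition.
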